5.3.2. Caffeine, Alcohol, and Tobacco

- Participants will abstain from caffeine-containing products for **≥ 24 hours** prior to the start of dosing until collection of the final PK sample in *each* study period (in Part 1 and Part 3) ***or*** last PK collection prior to discharge from the CRU (in Part 2);
- Participants will abstain from alcohol for **≥ 24 hours** prior (or as specified above for red wine) to admission to the CRU and continue abstaining from alcohol until collection of the final PK sample of each study period. Participants may undergo an alcohol breath test or blood alcohol test at the discretion of the investigator;
- Participants will abstain from the use of tobacco- or nicotine- containing products for **≥ 24 hours** prior to dosing and during confinement in the CRU.

5.3.3. Activity

- Participants will abstain from strenuous exercise (eg, heavy lifting, weight training, calisthenics, aerobics) for **≥ 48 hours** prior to each blood collection for clinical laboratory tests. Walking at a normal pace will be permitted;
- In order to standardize the conditions on PK sampling days, participants will be required to refrain from lying down (except when required for BP, pulse rate, and ECG measurements), eating, and drinking beverages other than water during the ***first 4 hours after dosing***;
- **In Part 1 only**, participants will be confined to the procedure room for the ***first 4 hours*** after dosing on Day 1 during continuous cardiac monitoring, except to use the bathroom. After this, if the equipment setup allows, participants may be ambulatory during the ECG monitoring period, but should not engage in strenuous activities. If equipment does not allow ambulation, appropriate accommodations will be made by the investigator site to facilitate continuous monitoring (eg, bedside urinals should be provided to accommodate participants' excretory needs);

- Participants will be advised to avoid direct sunlight exposure or any high intensity UV light exposure, from the first day of dosing with study intervention and until the on-site Follow-up visit. In addition, participants will be instructed to wear eye protection and apply sun cream/lotion with a high sun protection factor, as appropriate.

5.3.4. Contraception

The investigator or his or her designee, in consultation with the participant, will confirm that the participant has selected an appropriate method of contraception for the individual participant and his or her partner(s) from the permitted list of contraception methods (see [Section 10.4.4](#)) and will confirm that the participant has been instructed in its consistent and correct use. At timepoints indicated in the schedule of activities ([SoA-Table A](#), [SoA-Table B](#), and [SoA-Table D](#)), the investigator or designee will inform the participant of the need to use highly effective contraception consistently and correctly and document the conversation and the participant's affirmation in the participant's chart (participants need to affirm their consistent and correct use of at least 1 of the selected methods of contraception). In addition, the investigator or designee will instruct the participant to call immediately if the selected contraception method is discontinued or if pregnancy is known or suspected in the participant or partner.

5.4. Screen Failures

Screen failures are defined as participants who consent to participate in the clinical study but are not subsequently randomly assigned to study intervention/enrolled in the study. Screen failure data are collected and remain as source and are not reported to the clinical database.

Individuals who do not meet the criteria for participation in 1 of the 3 Parts of this study and are screen failed may be rescreened for a *different* Part of this 3-Part study.

6. STUDY INTERVENTION

Study intervention is defined as any investigational intervention(s), marketed product(s), placebo, medical device(s), or study procedure(s) intended to be administered to a study participant according to the study protocol.

For the purposes of this protocol, the term investigational product (ie, IP) may be used synonymously with study intervention and refers to all of the following:

- Placebo for PF-07202954;
- PF-07202954.

6.1. Study Intervention(s) Administered

For all parts of this study, PF-07202954 and placebo will be provided by Pfizer as bulk powders for extemporaneous preparation of oral suspension at the CRU.

PF-07202954 and placebo will be presented to the participants in individual dosing containers.

6.1.1. Administration

- **Part 1 and Part 2:** following an overnight fast of ≥ 10 hours, participants will receive the study intervention with a standard morning meal at approximately 08:00 hours (± 2 hours):
 - **NOTE:** if **up to 2** of the 8 periods in Part 1 are being utilized to assess plasma PK in the fasted state and/or with high-fat/high-caloric meal, dosing will occur in the appropriate/respective setting (ie, overnight fast of ≥ 10 hours or with high-fat/high-caloric meal).
- **Part 3:** following an overnight fast of ≥ 10 hours, participants will receive the study intervention either with water (fasted state) **or** with a high-fat/high-caloric meal at approximately 08:00 hours (± 2 hours), in each of the 2 Periods, per randomization assignment.

In all cases, investigator site personnel will administer study intervention during each period with ambient temperature water to a total volume of approximately 240 mL;

- Adequate measures to ensure taste masking will be performed **prior to** administration of the study intervention, if needed;
- Additional water (up to 120 mL) **may** be consumed by the participants (eg, extra rinse) in an attempt to ensure that the full dose is consumed – with such instances documented in the source at the site;
- Administration of study intervention will occur according to the EDR;
- In order to standardize the conditions on PK sampling days, all participants will be required to refrain from lying down (except when required for BP, pulse rate, and ECG measurements), eating, and drinking beverages other than water during the **first 4 hours after dosing**.

6.2. Preparation/Handling/Storage/Accountability

1. The investigator or designee must confirm appropriate temperature conditions have been maintained during transit for all study interventions received and any discrepancies are reported and resolved before use of the study intervention.
2. Only participants enrolled in the study may receive study intervention and only authorized site staff may supply or administer study intervention. All study interventions must be stored in a secure, environmentally controlled, and monitored (manual or automated recording) area in accordance with the labeled storage conditions with access limited to the investigator and authorized site staff. At a

minimum, daily minimum and maximum temperatures for all site storage locations must be documented and available upon request. Data for nonworking days must indicate the minimum and maximum temperatures since previously documented for all site storage locations upon return to business.

3. Any excursions from the study intervention label storage conditions should be reported to Pfizer upon discovery along with any actions taken. The site should actively pursue options for returning the study intervention to the storage conditions described in the labeling, as soon as possible. Once an excursion is identified, the study intervention must be quarantined and not used until Pfizer provides permission to use the study intervention. Specific details regarding the definition of an excursion and information the site should report for each excursion will be provided to the site in the PCRU local/site procedures.
4. Any storage conditions stated in the SRSD will be superseded by the storage conditions stated on the label.
5. Study interventions should be stored in their original containers.
6. See the EDR for storage conditions of the study intervention once prepared.
7. The investigator, institution, or the head of the medical institution (where applicable) is responsible for study intervention accountability, reconciliation, and record maintenance (ie, receipt, reconciliation, and final disposition records), such as the IPAL or sponsor-approved equivalent. All study interventions will be accounted for using a study intervention accountability form/record.
8. Further guidance and information for the final disposition of unused study interventions are provided in the PCRU's local/site procedures. All destruction must be adequately documented. If destruction is authorized to take place at the investigator site, the investigator must ensure that the materials are destroyed in compliance with applicable environmental regulations, institutional policy, and any special instructions provided by Pfizer.

Upon identification of a product complaint, notify the sponsor ***within 1 business day*** of discovery.

6.2.1. Preparation and Dispensing

Within this protocol, preparation refers to the investigator site activities performed to make the study intervention ready for administration or dispensing to the participant by qualified staff. Dispensing is defined as the provision of study intervention, concomitant treatments, and accompanying information by qualified staff member(s) to a healthcare provider, participant in accordance with this protocol. Local health authority regulations or investigator site guidelines may use alternative terms for these activities.

For Parts 1, 2, and 3: PF-07202954 and placebo oral dosing suspensions will be prepared in the CRU by 2 operators, 1 of whom is a pharmacist. Details of dose preparation will be given in a separate EDR. Prepared doses will be provided in unit dose containers and labeled in accordance with Pfizer regulations and the investigator site's labeling requirements.

For Parts 1 and 2: In order to maintain the blind, PF-07202954 and placebo will be prepared by qualified unblinded site personnel according to the EDR with study intervention administered in a blinded fashion to the participant.

6.3. Measures to Minimize Bias: Randomization and Blinding

6.3.1. Allocation to Study Intervention

The investigator will assign participant numbers to the participants as they are screened for the study. Pfizer will provide a randomization schedule to the investigator and, in accordance with the randomization numbers, the participant will receive the study treatment regimen assigned to the corresponding randomization number.

Participants will be randomly assigned to receive study intervention from a central randomization scheme. ***In Part 1 and Part 2***, investigators will remain blinded to each participant's assigned study intervention throughout the course of the study. In order to maintain this blind, an otherwise uninvolved third party (for example, a pharmacist) will be responsible for the preparation and dispensing of all study intervention according to the randomization schedule and assigned treatment for the individual participant.

For Part 3, the investigator's knowledge of the treatment should not influence the decision to enroll a particular participant or affect the order in which participants are enrolled.

6.3.2. Breaking the Blind – Part 1 and Part 2, only

The method for breaking the blind will be manual. In case of an emergency, the investigator has the sole responsibility for determining if unblinding of a participant's treatment assignment is warranted. Participant safety must always be the first consideration in making such a determination. If the investigator decides that unblinding is warranted, the investigator should make every effort to contact the sponsor prior to unblinding a participant's treatment assignment unless this could delay further management of the participant. If a participant's treatment assignment is unblinded, the sponsor must be notified ***within 24 hours*** after breaking the blind. When the blinding code is broken, the reason must be fully documented and entered on the DCT.

Blood specimens will be obtained from all participants for PK analysis to maintain the study blind at the investigator site. Only the investigator site staff and blinded study monitor, if assigned, will be blinded to study treatment. A ***limited number*** of the sponsors' study team personnel will be unblinded to participant treatments in order to permit real-time interpretation of the safety and PK data; and provide information necessary to potentially alter the dose-escalation sequence. The blinded study monitor, if assigned, will remain blinded to treatment until all monitoring for the study has been completed. Specimens from

participants randomized to placebo will not be routinely analyzed. To minimize the potential for bias, treatment randomization information will be kept confidential by Pfizer unblinded personnel and will not be released to the blinded investigator or blinded investigator site personnel until the study database has been locked or the investigator requests unblinding for safety reasons.

6.4. Study Intervention Compliance

In Part 1, Part 2, and Part 3, when participants are dosed at the site, they will receive study intervention directly from the investigator or designee, under medical supervision. The date and time of each dose administered in the clinic will be recorded in the source documents and recorded in the DCT. The dose of study intervention and study participant identification will be confirmed at the time of dosing by a member of the study site staff.

6.5. Concomitant Therapy

Use of prescription or nonprescription drugs and dietary and herbal supplements are prohibited within **7 days or 5 half-lives** (whichever is longer) prior to the first dose of study intervention –

- Limited use of nonprescription medications that are not believed to affect participant safety or the overall results of the study may be permitted on a case-by-case basis following approval by the sponsor;
- Acetaminophen/paracetamol may be used at doses of ≤ 1 gram per day;
- Females using estrogen containing hormonal contraceptives or taking estrogen containing HRT may be eligible to participate in this study *if they are willing to discontinue therapy ≥ 28 days* prior to the first dose of study intervention and remain off hormonal therapy for the duration of the study:
 - Depo-Provera[®] must be discontinued **at least 6 months** prior to the first dose of study intervention.

All concomitant treatments taken during the study must be recorded with indication, daily dose, and start and stop dates of administration. All participants will be questioned about concomitant treatment at each clinic visit.

Treatments taken ***within 28 days before the first dose of study intervention*** will be documented as a prior treatment. Treatments taken after the first dose of study intervention will be documented as concomitant treatments.

6.6. Dose Modification

The dosing schedule may be adjusted to repeat 1 or more dose level(s) to further evaluate safety, tolerability, or plasma PK of PF-07202954, and/or explore markers of clinical activity at a given dose level or to add cohorts to evaluate additional dose levels – as described in **Section 4.3**. The study procedures for these additional participant(s)/cohort(s) will be the same as that described for other study participants/cohorts in this protocol.

6.6.1. Dose-Escalation and Stopping Rules

Dose-escalation stopping rules will be used to determine whether the maximal tolerated dose has been attained. Dose-escalation may be stopped if it is determined that the limits of safety and/or tolerability have been reached. This decision will be made after a discussion takes place between the sponsor study team and the investigator. The sponsor study team may not overrule the investigator's decision to stop dose-escalation. If dose-escalation is stopped because of any of these criteria, additional cohorts may receive the same or lower doses of the study intervention.

The dose-escalation in Part 1 ***and*** separately in Part 2 will be terminated based on the following criteria:

- If **50% or more** of the participants receiving active drug at a given dose level (but not participants receiving placebo) develop similar clinically significant laboratory, ECG, or vital sign abnormalities, in the same organ class, indicating dose-limiting intolerance.
- Severe nonserious AEs, considered as, at least, possibly related to study intervention administration, in 2 participants at a given dose level (but not participants receiving placebo), independent of within or not within the same system organ class, indicating dose-limiting intolerance.
- Dosing will be paused for any SAE that occurs in a participant receiving active treatment until causality is fully assessed by the PI and sponsor. Dosing may resume if the SAE is determined to be not drug-related by the PI and sponsor. If the SAE is determined to be either drug-related or unknown, either dosing will cease or the SAE will be evaluated by the sponsor's protocol review committee (or similar review group), which is independent of the study team and investigators. If the protocol review committee determines that dosing may resume, a plan that mitigates risks to participants with the resumption of dosing will be implemented. Such a plan could include a revision of inclusion/exclusion criteria, repeating or reducing the dose, or adding appropriate safety monitoring.
- It is determined that the limit of safety and/or tolerability has been reached. This decision will be made following discussions between the study team and the investigator.

- Other findings that, at the discretion of the study team and investigator, indicate that dose-escalation should be halted.
- If, at any dose level, the average exposure reaches or exceeds the PK stopping limits defined as the following:
 - total C_{max} =1450 ng/mL (in Part 1 and Part 2);
 - total AUC_{24} =18,400 ng•h/mL (in Part 1);
 - total AUC_{24} =3,680 ng•h/mL (in Part 2 with revision to this stopping limit to be considered, via a protocol amendment post formal interim analysis, based on observed data in Part 1 *and* Part 2 in this study).
- If, based on the observed data, the group mean C_{max} or AUC (based on total plasma concentration) of the next planned dose is projected to exceed the escalation limits, that dose will not be explored. Modified doses may be explored if they are not expected to exceed PK stopping criteria.

Progression to the next dose level will occur if the last dose was well tolerated and after satisfactory review of the available safety and PK data.

- **Part 1:** A minimum of 6 participants (including at least 1 participant who received placebo) of the planned 8 participants to be dosed at each dose level must complete dosing and planned assessment to a minimum of 24 hours post dose. Safety, tolerability, and plasma PK data through ***at least 24 hours post dose*** for the prior dose level (along with cumulative data from all previously administered doses) will be reviewed in order to identify the next dose-level to escalate to in the next period.
- **Part 2:** A minimum of 8 participants (including at least 1 participant who received placebo) of the planned 10 participants to be dosed at each dose level must complete the planned 14 days of dosing and planned safety/tolerability assessments to a ***minimum of 24 hours post dose on Day 14***.
 - In addition, plasma PK data through ***at least 24 hours post dose on Day 7 (or*** at least 24 hours post dose on Day 14 ***if*** the observed $t_{1/2}$ of PF-07202954 in Part 1 is greater than 30 hours) for the prior dose level (along with cumulative data from all previously administered doses) will be reviewed in order to identify the next dose-level to escalate to in the next period.

6.7. Intervention After the End of the Study

No intervention will be provided to study participants at the end of the study.

7. DISCONTINUATION OF STUDY INTERVENTION AND PARTICIPANT DISCONTINUATION/WITHDRAWAL

7.1. Discontinuation of Study Intervention

In rare instances, it may be necessary for a participant to permanently discontinue study intervention (definitive discontinuation). Reasons for definitive discontinuation of study intervention include the following: AE, or some other (administrative) reason.

If study intervention is definitively discontinued, the participant will *not* remain in the study for further evaluation. See the [SoA-Table A](#), [SoA-Table B](#), and [SoA-Table D](#) for data to be collected at the time of discontinuation of study intervention.

In the event of discontinuation of study intervention, it must be documented on the appropriate CRF/in the medical records whether the participant is discontinuing further receipt of study intervention or also from study procedures, posttreatment study follow-up, and/or future collection of additional information.

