3. OBJECTIVES AND ENDPOINTS

Table 2 outlines the key objectives and endpoints for Part 1, Part 2, and Part 3 (if conducted) of this study.

Table 2. Key Objectives and Endpoints in Study C4171001

Study	Objectives	Endpoints
Part 1		
Primary	To evaluate safety and tolerability of single , oral, escalating doses of PF-07202954 administered with a standard morning meal in healthy, adult participants.	Following assessments over ≥ 10 days of each Period and up to Day 30 ± 2 days post last dose of study intervention – 
• AEs;• Clinical laboratory tests;• Vital signs (including BP and pulse rate);• Cardiac conduction intervals via 12-lead ECG.
Secondary	To characterize the plasma PK profile of PF-07202954 following administration of single , oral, escalating doses.	PK parameters ^a derived from plasma PF-07202954 concentrations: 
• C_{max}, T_{max}, AUC_{last}, AUC_{inf}, $t_{1/2}$, as data permit.
Part 2		
Primary	To evaluate safety and tolerability of repeated , oral, escalating doses of PF-07202954 administered with a standard morning meal in healthy, adult participants with simple hepatic steatosis.	Following assessments over the duration of dosing and up to Day 30 ± 2 days post last dose of study intervention – 
• AEs;• Clinical laboratory tests;• Vital signs (including BP and pulse rate);• Cardiac conduction intervals via 12-lead ECG.
Secondary	To characterize the plasma and urine PK profiles of PF-07202954 following administration of repeated , oral, escalating doses.	PK parameters ^a derived from plasma PF-07202954 concentrations: 
• Single dose: C_{max}, T_{max}, AUC_{tau} on Day 1.

Table 2. Key Objectives and Endpoints in Study C4171001

Study	Objectives	Endpoints
		
Repeated dose:
Days 7 and 14 – C_{max}, T_{max}, AUC_{tau}, as data permit.Day 14 – $t_{1/2}$ as data permit. 
PK parameters^a derived from urine PF-07202954 concentrations on Day 14: Ae_{tau}, $Ae_{tau}\%$, CL_r.

Part 3, if conducted		

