7.1.1. ECG Changes

A participant who meets either of the bulleted criteria below based on the average of triplicate ECG readings will be withdrawn from the study intervention.

- QTcF >500 msec.
- Change from baseline: QTcF >60 msec.

If a clinically significant finding is identified (including, but not limited to, changes from baseline in QTcF after enrollment), the investigator or qualified designee will determine if the participant can continue in the study and if any change in participant management is needed. This review of the ECG printed at the time of collection must be documented. Any new clinically relevant finding should be reported as an AE.

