7.1.2. Potential Cases of Acute Kidney Injury

Abnormal values in SCr and SCysC concurrent with presence or absence of increase in BUN that meet the criteria below, in the absence of other causes of kidney injury, are considered potential cases of acute kidney injury and should be considered important medical events.

An increase of ≥ 0.3 mg/dL (or ≥ 26.5 μ mol/L) in SCr level and increase of $\geq 30\%$ in SCysC level relative to the participant's own baseline measurement should trigger another assessment of SCr and SCysC as soon as practically feasible, preferably ***within 48 hours from awareness***.

If the second SCr assessment (after the first observations of ≥ 0.3 mg/dL [or ≥ 26.5 $\mu\text{mol/L}$] in SCr increase relative to the participant's own baseline measurement) is ≥ 0.4 mg/dL (or ≥ 35.4 $\mu\text{mol/L}$), **and** if the second SCysC assessment (after the first observation of $\geq 30\%$ increase relative to the participant's baseline measurement) remains increased by $\geq 30\%$, then further dosing of study intervention should be withheld. The participant should continue all safety assessments and adequate, immediate, diagnostic, and supportive measures taken to correct apparent acute kidney injury.

If a participant demonstrates concomitant SCr-based **and** SCysC-based eGFR decline of $\geq 30\%$ compared to the participants' baseline concomitant SCr-based **and** SCysC-based eGFR, then the participant should not be further dosed and adequate, immediate, supportive measures including **urgent evaluation by a nephrologist (preferably within 24 hours) with appropriate management** and treatment as clinically indicated. Safety assessments should be repeated weekly or as indicated by the nephrologist until the renal parameters are deemed to be stable by the nephrologist and/or PI.

If the participant cannot be seen by a nephrologist within 24 hours (as described above), then the participant should be sent to a local emergency room for evaluation and treatment as clinically indicated.

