8.3.1. Time Period and Frequency for Collecting AE and SAE Information

The time period for actively eliciting and collecting AEs and SAEs (“active collection period”) for each participant begins from the time the participant provides informed consent, which is obtained before the participant’s participation in the study (ie, before undergoing any study-related procedure and/or receiving study intervention), through and including ***a minimum of 28 calendar days***, except as indicated below, after the last administration of the study intervention.

Follow-up by the investigator continues throughout and after the active collection period and until the AE or SAE or its sequelae resolve or stabilize at a level acceptable to the investigator and Pfizer concurs with that assessment.

For participants who are screen failures, the active collection period ends when screen failure status is determined.

If the participant withdraws from the study and also withdraws consent for the collection of future information, the active collection period ends when consent is withdrawn.

If a participant definitively discontinues or temporarily discontinues study intervention because of an AE or SAE, the AE or SAE must be recorded on the CRF and the SAE reported using the CT SAE Report Form.

Investigators are not obligated to actively seek AE or SAE after the participant has concluded study participation. However, if the investigator learns of any SAE, including a death, at any time after a participant has completed the study, and he/she considers the event to be reasonably related to the study intervention, the investigator must promptly report the SAE to Pfizer using the CT SAE Report Form.

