### **3.5.1. Treatment Emergent Adverse Events**

Any events occurring following start of treatment (either PF-07202954 or placebo) will be counted as treatment emergent. Events that occur in a non-treatment period (i.e. follow-up) within the lag time of 28 days will be counted as treatment emergent and attributed to the previous treatment taken. Similarly, the time period for collecting AEs (“active collection period”) for each participant begins from the time the participant provides informed consent.

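### Protocol 7.1 takes participants whose dosing is stopped, including for an AE, out of the study at the D/C visit; this conflicts with the protocol's own follow-up rules, and Parts 1 and 3 give such participants no follow-up date

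*Protocol*

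**What the plan says.** Protocol 7.1 gives AEs and administrative reasons as grounds for definitive discontinuation of study intervention. It then says that "the participant will *not* remain in the study for further evaluation" and refers to the Schedule of Activities (SoA) for what is collected at that time.

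Other parts of the plan bear on the same participant:

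- **7.1, next paragraph.** The site must record "whether the participant is discontinuing further receipt of study intervention or also from study procedures, posttreatment study follow-up".
- **7.1.2, eGFR rule.** A concomitant decline of at least 30% in creatinine-based and cystatin-C-based eGFR ends dosing. After that, "Safety assessments should be repeated weekly or as indicated by the nephrologist until the renal parameters are deemed to be stable".
- **8.3.1.** Active AE collection for each participant lasts at least 28 calendar days, "except as indicated below, after the last administration of the study intervention". The early ends it names are screen failure and withdrawn consent. The same section also says "Investigators are not obligated to actively seek AE or SAE after the participant has concluded study participation".
- **Section 3, Table 2.** The safety endpoint runs to Day 30±2 "days post last dose of study intervention". It is primary in Parts 1 and 2 and secondary in Part 3.
- **7.2.1.** Participants who themselves ask to stop drug stay in the study and are followed.
- **7.2.** After the early discontinuation visit the participant is off both drug and study.
- **SoA follow-up footnotes.** Table A (Part 1) times both contacts from the Period 4 dose and Table D (Part 3) from the Period 2 dose. Table B (Part 2) times them from the last dose and glosses this as Day 22±2 and Day 44±2.

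**The concern.** A site cannot take a participant out of the study when dosing stops and also carry out weekly renal assessments, 28 days of active AE collection and a contact at Day 30±2. Two sites with the same case could reasonably act differently, and each could cite the protocol.

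This is a first-in-human study in which safety and tolerability form the primary objective of Parts 1 and 2. Each dose level has 6 (Part 1) or 8 (Part 2) participants on active drug, so one participant stopped for an AE is 1/6 (about 17%) or 1/8 (12.5%) of the active safety evidence at that dose. Read literally, 7.1 gives that person the D/C assessments, which include laboratory tests, ECG and vital signs, but neither the on-site visit at 8±2 days nor the telephone contact at 30±2 days. The contrast with 7.2.1 is awkward: someone who chooses to stop drug is followed, and someone stopped for an AE is not.

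**Working it through.** The documents give no figure for this point, so the check compares texts and does simple date arithmetic.

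**Step 1. Which texts conflict with 7.1?**

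| Text | Can it hold together with the 7.1 sentence? |
|---|---|
| 7.1, next paragraph | No. A choice between stopping drug only and also stopping follow-up is empty if everyone leaves. |
| 7.1.2, eGFR rule | No. Dosing ends but repeat safety assessments continue. (The creatinine/cystatin C rule before it says only that dosing is withheld, which may be temporary, so it is not relied on.) |
| 8.3.1, 28-day minimum | No. It covers each participant and mentions definitive discontinuation for an AE without giving that case an early end. |
| Table 2, Day 30±2 | The endpoint stands, but its window goes unfilled for early stoppers. |
| 7.2.1 | Takes the opposite line, for a different route to stopping (the participant's own request). |
| 7.1.1 | Yes. Context only; see the objection. |
| SAP 3.5.1 | Yes. Context only; see the objection. |

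Section 8.3.1 does not settle the matter alone. It also lifts the duty to seek AEs once participation has concluded, which is the status 7.1 gives an early stopper.

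**Step 2. What is lost if 7.1 is followed literally?**

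Inputs: on-site window 8±2, which is days 6 to 10 after the last dose; telephone window 30±2, which is days 28 to 32; AE minimum 28 days. The documents do not say when the D/C visit takes place. Assume day d after the last dose, with d = 0, d = 3 (72 hours, the last inpatient timepoint in Part 1) or d = 10 (the minimum gap between Part 1 doses).

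- Time by which the last laboratory tests, ECG and vital signs precede the planned on-site visit = (6 − d) to (10 − d).
- Shortfall in active AE enquiry = 28 − d.

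| d | Assessments earlier than planned by | AE enquiry short by |
|---|---|---|
| 0 | 6 to 10 days | 28 days |
| 3 | 3 to 7 days | 25 days |
| 10 | none (inside the window) | 18 days |

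**Step 3. Is there a follow-up date?**

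- Part 1: anyone stopping after Period 1, 2 or 3 has no Period 4 dose. If a site used the planned Period 4 date at the minimum 10-day spacing (an assumption), a Period 1 stopper's contacts would fall at 3×10 + 8 = 38±2 and 3×10 + 30 = 60±2 days after the actual last dose.
- Part 3: anyone stopping after Period 1 has no Period 2 dose. At the minimum 5-day spacing, the same workaround gives 5 + 8 = 13±2 and 5 + 30 = 35±2 days.
- Part 2: the anchor is correct. The gloss is 14 + 8 = 22 and 14 + 30 = 44, so it fits only a last dose on Day 14.

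**Step 4. Does timing from the participant's own last dose repair this?** The earliest telephone contact is then day 30 − 2 = 28. That meets the 28-day AE minimum and falls within the Day 30±2 endpoint window.

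**The case against.** The best defence is that 7.1 is deliberate. The word 'not' is emphasised, 7.2 ends with the participant off both drug and study, the abbreviation list (10.8) defines D/C as leaving the study, and the SoA has a D/C column beside the follow-up columns. On that reading completers take the follow-up contacts, early stoppers take D/C, and the Period 4 and Period 2 anchors are simply footnotes for completers. This is a coherent reading of the SoA. It does not reconcile 7.1 with its own next paragraph, with the eGFR rule or with the 28-day minimum, and no rationale for it is given.

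It can also be said that a specific renal rule overrides a general one, so renal follow-up could run outside scheduled visits. That may be what a sensible site would do, but 7.1 does not say so.

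Other parts of the defence stand in full:

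- **7.1.1 is not a contradiction.** Its statement that "the investigator or qualified designee will determine if the participant can continue in the study" covers any clinically significant ECG finding, including ones that do not require stopping drug.
- **SAP 3.5.1 is not a contradiction.** Events "within the lag time of 28 days will be counted as treatment emergent", which is a counting rule; it orders no visit.
- **Known problems are followed.** Section 8.3.3 follows known AEs. Section 8.2.4 requires clinically significant laboratory abnormalities, during participation or within 14 days after the last dose, to be repeated until resolved.
- **Late drug exposure should be small.** With the projected half-life of about 8 hours, 72 hours is 72/8 = 9 half-lives. This is a projection, not an observation.

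A reader might infer that participants with AEs are abandoned, or that a whole type of safety assessment is lost. The documents do not support either. The D/C visit includes laboratory tests, ECG and vital signs, and 8.2.4 and 8.3.3 continue afterwards.

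**Conclusion.** The conflict is real and should be fixed. Section 7.1 states a rule that, followed literally, disagrees with its own next paragraph, the eGFR rule in 7.1.2 and the 28-day AE minimum in 8.3.1, and leaves the Day 30±2 safety window unfilled for early stoppers. In Parts 1 and 3 the SoA gives them no date from which to time follow-up.

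The consequence is narrow. It concerns new or late findings after the D/C visit, in AE and administrative stoppers alike, and inconsistent handling between sites. The shortfall of 28, 25 or 18 days in active AE enquiry rests on two assumptions: the D/C visit falls on day 0, 3 or 10, and the site lets 7.1 override 8.3.1. A site that lets 8.3.1 govern loses no AE collection.

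The number of participants affected cannot be stated: no discontinuation rate is given, and 7.1 itself expects such stops to be rare. A reader might also infer that dose-escalation decisions are compromised. They are not: the minimum data requirement in 6.6.1 ends 24 hours after the dose (Part 1) or 24 hours after the Day 14 dose (Part 2), and does not depend on these follow-up contacts.

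**What to change.** 1. **7.1.** Replace the sentence with a rule that a participant who definitively stops drug completes the SoA D/C assessments and then, unless he or she refuses follow-up or withdraws consent, the on-site contact (8±2 days) and the telephone contact (30±2 days), both timed from his or her own last dose. State that a D/C visit on days 6 to 10 counts as the on-site visit, so that it is not duplicated.
2. **SoA Tables A and D, footnote a.** Change the anchor from Period 4 and Period 2 to the participant's own last dose.
3. **SoA Table B, footnote b.** Mark Day 22±2 and Day 44±2 as applying to those who complete 14 days of dosing.
4. **7.2 and the D/C entry in 10.8.** At present both tie the D/C visit to leaving the study. Extend them to cover people who stop drug only, and limit the closing off-drug-and-off-study sentence of 7.2 to those who leave the study. Without this, step 1 would create a new inconsistency.

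The rules for when dosing stops do not change. The cost is a handful of wording changes, plus at most one extra on-site visit and one telephone call for each of a few early stoppers. Both contacts already exist in the schedule.
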